7.4 Screen Failures

Data for screen and baseline failures will be collected in source documentation at the sites but will not be transmitted to AOBiome.

7.5 Early Termination

Participants who have discontinued the study early will be evaluated by the Investigator at the Unanticipated Visit. See the list of assessments to be performed at the Unanticipated Visit in the Schedule of Events Table (Appendix A). Participants with ongoing AEs or SAEs believed to be possibly related to investigational product (IP) will continue to be followed until resolution or for 30 days as warranted by the nature of the AE.

8 STUDY TREATMENT

8.1 Investigational Product

Under normal conditions of handling and administration, IP is not expected to pose significant safety risks to site staff. A Material Safety Data Sheet describing the occupational hazards and recommended handling precautions will be provided to site staff if required by local laws or will otherwise be available from the Sponsor upon request.

Investigational product must be stored in a secure area under the appropriate physical conditions for the product. Access to and administration of the IP will be limited to the Investigator and authorized site staff. Investigational product must be dispensed or administered only to participants enrolled in the study and in accordance with the protocol.

The Investigator is responsible for study treatment accountability, reconciliation, and record maintenance. The Investigator or designated site personnel must maintain study treatment accountability records throughout the course of the study. The responsible person(s) will document the amount of study treatment received from and returned to the sponsor and the amount administered to participants. The required accountability unit for this study will be the bottle. Discrepancies are to be reconciled or resolved.

Product name:	B244, 30ml/bottle	B244, 30ml/bottle	Placebo, 30ml/bottle
Dosage form:	B244 suspension	B244 suspension	Vehicle solution
Unit dose strength:	1×10^9 cells/ml	4×10^9 cells/ml	50nM Na ₂ HPO ₄ -

			2mM MgCl ₂ (pH 7.6)
Route/administration/duration:	Intranasal application: Part 1: 1 pump (140ul) per nostril BID for 14 days Part 2: 1 pump (140ul) per nostril BID for 14 days	Intranasal application: Part 1: 1 pump (140ul) per nostril BID for 14 days Part 2: 1 pump (140ul) per nostril BID for 14 days	Intranasal application: Part 1: 1 pump (140ul) per nostril BID for 14 days Part 2: 1 pump (140ul) per nostril BID for 14 days
Dosing instruction:	Prime the spray with 5 actuations (pumps) into air prior to first use only. Apply 1 pump per nostril (2 pumps total) in the morning and repeat (2 additional pumps) at night for 14 days of treatment.	Prime the spray with 5 actuations (pumps) into air prior to first use only. Apply 1 pump per nostril (2 pumps total) in the morning and repeat (2 additional pumps) at night for 14 days of treatment.	Prime the spray with 5 actuations (pumps) into air prior to first use only. Apply 1 pump per nostril (2 pumps total) in the morning and repeat (2 additional pumps) at night for 14 days of treatment.
Physical description:	Odorless, cloudy, light pink suspension	Odorless, cloudy, light pink suspension	Odorless, clear, and colorless suspension
Manufacturer/source of procurement:	AOBiome, LLC	AOBiome, LLC	AOBiome, LLC

The contents of the label will be in accordance with all applicable regulatory requirements. B244 and matching placebo will be packaged in identical 30 ml white bottles.

8.2 Dose Changes

No dose changes are anticipated.

8.3 Storage Conditions

All investigational drug supplies in the study will be stored in a secure, refrigerated (2-8°C) safe place, under the responsibility of the Investigator or other authorized individual prior to randomization and distribution to participants. Once subjects are sent home with investigational product at visit 2 and visit 3 for Part 1 and Part 2 phases of the study, respectively, subjects will store the investigational product (IP) in room temperature (20-25 °C) during use at home on the counter, being mindful to avoid extreme temperatures and areas of excessive heat (e.g., inside the car or trunk during heat) or cold (i.e., do not freeze).

8.4 Description of Blinding Method

This study will be double-blind: neither Investigator(s), nor study participants, nor those involved in the conduct of the trial (including sponsor staff) will be aware of the treatment the participants are receiving.

8.5 Treatment Assignments:

This is a double blind study. Randomization will be stratified by site.

When a subject completes the screening tests and procedures, the investigator will notify the Site's pharmacist and the subject will be randomly assigned to one of three treatment groups in a 1:1:1 ratio. Randomization and treatment assignment will be verified and coordinated by the Site's pharmacist.

Each participant scheduled to receive investigational product (IP) will receive a randomization number at the time of randomization. The randomization number will be used to identify the study medication kit assigned to the participant and indicate the treatment to be administered to that participant.

8.6 Treatment Compliance

Study treatment must be dispensed or administered according to procedures described herein. Only participants enrolled in the study may receive study treatment. Only authorized site personnel may supply study treatment. Participants will record use of the study medication utilizing the study diary at the time of use each day. Participants will review study medication compliance with the Investigator or designee. Any missed doses, timing, and reason for missed dose will be recorded in the eCRF. There should be no doubling of doses to make up for missed doses. If a dose is missed, the next dose of study medication should be taken as scheduled.

Each site participating in the trial will be instructed to assess subject's compliance by weighing the investigational product and obtaining the weight of the bottle in grams pre and post application during Part 1 (at Visits 2 and 3) as well as during Part 2 (at Visits 3 and 4). Sites will be provided scales, which will be calibrated prior to each use. Study personnel will be instructed to record measurements into the eCRF.

8.7 Treatment Application

Subjects will receive one 30 ml bottle at the Baseline visit (Visit 2) for a 14 day application in Part 1. Subjects will receive one 30 ml bottle at the NAC #1 visit (Visit 3) for a 14 day application in Part 2. Subjects will be instructed in the use of the spray bottle and asked to self-administer the Investigational Product as follows:

- ☒ Spray 1 pump of medication into each nostril twice a day for 14 days

Detailed Investigational Product nasal spray instructions are as follows:

- Shake bottle gently
- Prime nozzle if unused; Pump until mist appears (5 times)
- Place nozzle straight up one nostril and pump once
- Sniff gently after spraying
- Repeat other nostril
- Wipe spray nozzle with tissue when done
- Do not wash/rinse the application site or blow their nose *for 30 min* after applying the mist

In Part 1, subjects will be asked to report for a screening visit and if all inclusion/exclusion criteria are met, subjects will be asked to report for a baseline visit and randomization. Subjects will then be trained on the use of the nasal spray, and have their first dose of treatment on site. Subjects will remain onsite for observation for 1 hour post dosing. Subjects will then be dispensed study medication for 14 days of at home dosing. While at home, subjects will dose twice daily (am and pm), and record their dosing, any occurrence of an AE, and Total Nasal Symptom Score (TNSS) using a study diary. Subjects will be asked to visit the site at Day 14 (Week 2) and at follow-up visits at Day 21 (Week 3) and Day 42 (Week 6) for safety assessments and will additionally record Peak Nasal Inspiratory Flow (PNIF), intranasal fluid, intranasal nitric oxide (nNO) and nasal inflammation score.

In Part 2, subjects will be asked to report for a screening visit (Visit 1) and if all inclusion/exclusion criteria are met, subjects will be asked to report for a NAC titration (ragweed pollen nasal allergen titration) visit to administer a single provocative challenge dose for each subject (Visit 2). Subjects will then return 14 days after the washout period for basic health checks and baseline assessments (intranasal fluid, TNSS, PNIF, intranasal nitric oxide, and have a nasal inflammation score) followed by confirmatory NAC (NAC#1) (Visit 3). During this time subjects will use a study diary to complete TNSS at -30 (30 minutes prior to NAC), 0 (baseline prior to NAC), 15, 30, 45, 60, 90, and 120 minutes. PNIF at -30, 0, 15, 30, 60, and 120 minutes will also be obtained. TNSS is the sum of four individual symptom scores (running nose, congestion, itchy nose, and sneezing) rated on a four point scale (0-3). Subjects are required to meet the minimum qualifying TNSS score of a change of 6/12 from their baseline score, on at least 2 diary cards. Subjects will also provide samples for intranasal fluid at 0, 20, and 60 minutes, measure intranasal nitric oxide (nNO) and have a nasal inflammation score assessed by the investigator using a nasal otoscope at 0 and 120 minutes, in addition to blood collection at 120 min for biomarkers. Subjects meeting the requirement will be randomized to one of the three treatment arms. Randomization will be 1:1:1 so that equal number of subjects will be treated in each arm of the study. Subjects will then be trained on the use of the nasal spray, and have their first dose of treatment on site (self-dosing). Subjects will remain onsite for observation for 1 hour post dosing. Subjects will then be dispensed study medication for 14 days of at home

dosing. While at home, subjects will dose twice daily (am and pm), and record their dosing, and any occurrence of an AE and TNSS using a study diary. Subjects will return to the clinic for the last dose following the 14 days of at home dosing for their final visit (Visit 4). During this time subjects will again have their baseline assessments and be exposed to ragweed pollen challenge (NAC#2), and will use a study diary to complete TNSS at -30, 0, 15, 30, 45, 60, 90, and 120 minutes and PNIF at -30, 0, 15, 30, 60, and 120 minutes. Prior to and 20 and 60 minutes after NAC #2, subjects will additionally provide samples for intranasal fluid, and have nNO measured and have a nasal inflammation score assessed by the investigator using a nasal otoscope at 0 and 120 min, in addition to blood collection at 120 min for biomarkers.

8.8 Treatment of Investigational Product Overdose

The sponsor does not recommend specific treatment for an overdose.

8.9 Product Accountability

In accordance with federal and local regulatory requirements, the Investigators and designated site personnel must document the amount of investigational product dispensed to study participants, the amount returned by study participants, and amount received and returned to the sponsor, when applicable. Product accountability records must be maintained throughout the course of the trial. Any quality issue noticed with the receipt or use of an IP (deficient IP in condition, appearance, pertaining documentation, labeling, expiry date, etc.) should be promptly reported to the Sponsor, who will initiate a complaint procedure.

All investigational product must be stored in a secure locked room with access limited to the Investigator and designated site personnel. Study product is to be stored in a refrigerator between 2-8 degrees C. Maintenance of a temperature log is required.

Under no circumstances will the Investigator allow IP to be used other than as directed by this Clinical Trial Protocol, or dispose of IP in any other manner.

8.10 Unblinding Procedures

The Investigator may unblind a participant's treatment assignment only in the case of emergency or in the event of a serious medical condition when knowledge of the study treatment is essential for the appropriate clinical management or welfare of the participant, as determined by the Investigator. It is preferred (but not required) that the Investigator first contacts the medical monitor to discuss options before unblinding the participant's treatment assignment. The Investigator must notify the Sponsor as soon as possible when a participant's treatment assignment is unblinded without revealing the treatment assignment of the unblinded participant unless that information is deemed important for the safety of participants currently in the study. The date and reason for the unblinding must be documented in the participant's study record.

The Medical Monitor may unblind the treatment assignment for any participant with an SAE. If the SAE requires that an expedited regulatory report be sent to one or more regulatory agencies, a copy of the report, identifying the participant's treatment assignment, may be sent to clinical Investigators in accordance with local regulations and/or sponsor policy.

8.11 Retrieval and Destruction of Investigational Product

All partially used or unused treatments will be returned to the sites as brought by study participants. A detailed treatment log of the returned IP shall be established.

The sites will not destroy unused IP unless the Sponsor provides written authorization to the contrary. All used and unused bottles will be shipped to the authorized drug depot at the end of the study.

8.12 Permitted Medications

All participants will be screened for concomitant medications prior to inclusion into the study. Any concomitant medication to treat adverse events will be recorded in the Concomitant Medication section of the eCRF.

8.13 Prohibited Medications

Participants will be prohibited from taking antihypertensives, beta blockers, photosensitising medications, systemic immunosuppressants and vitamin D supplements. NSAIDs or corticosteroids are also prohibited as they may affect BP. Additional prohibited medications include antihistamines, leukotriene modifying medications, cromolyn, environmental allergen immunotherapy, Omalizumab, antibiotics, and any intranasally administered over-the-counter product or nasal irrigation (e.g., neti pot). Complete list of prohibited medications will be provided to the site PIs conducting the study.

8.14 Rescue Medications

Rescue medications will not be allowed during the study. Subject may not start additional non-randomized medication and should immediately alert the study site PI. Subjects that need to start new rescue medication regimen should be immediately discontinued from study participation and would be considered Early Termination.

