10.6.5 Unscheduled/Unanticipated Study Visit

If an event arises that requires patient to come in to the research center, subjects should be scheduled for the Unscheduled visit.

During the visit, the following will be obtained:

- medical/surgical history
- record concomitant medications
- obtain in clinic blood pressure, heart rate, respiratory rate
- physical exam
- body weight
- nasal inspection
- obtain study medication weight for Investigational Product compliance
- study counseling
- laboratory testing (blood for metabolic panel, hematology, clinical chemistry, liver function test, urinalysis)
- study AEs
- nasal fluid collection for biomarkers
- blood collection for biomarkers
- peak nasal inspiratory flow (PNIF)
- intranasal nitric oxide
- nasal inflammation score
- study diary

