12.2 Safety Monitoring

Local and systemic adverse events (AEs) related to intranasal route of administration during 14 days of treatment and 28 days of follow-up (7 and 28 days after the last dose of the study) will be recorded for the safety phase of the study in healthy volunteers (Part 1). Additionally, local and systemic AEs will be recorded in subjects with a history of seasonal allergic rhinitis during the efficacy phase of the trial (Part 2).

Safety monitoring will include infectious complications related to B244 (by symptoms and/or testing; pulmonary, nasal, neurological), local and systemic AEs related to intranasal route during treatment and at follow-up. Local AEs include runny nose, nasal congestion, sneezing, nasal itching, palate itching, anosmia, nasal ulceration, nasal bleeding, sore throat, cough, Bell's palsy, other neurologic complications, fevers, chills, headache, muscle aches, decreased appetite, nausea, vomiting, and rash.

Sponsor will distinguish between immediate (onset of reaction is during the first 30 minutes after administration) and delayed (onset of action is after the first 30 minutes of administration) effects for safety reporting of adverse events.

Due to the nature of the nasal allergen challenge (in Part 2 of the study) which consists of delivering allergen directly into the airways of an allergic individual, a medical doctor trained for treating anaphylaxis must be present within the building. A crash cart and the crash team telephone number must be readily available. The nasal allergen challenge involves spraying a solution with very small amounts of ragweed antigen (allergy causing substance) into the nose. The side effects of this can be nasal blockage, excessive nasal discharge (similar to seasonal allergy symptoms), which may be delayed by several hours. There is also a risk of bronchoconstriction (wheezing), especially if one has a history of asthma. The most serious risk of having a nasal challenge test is anaphylactic reaction. This reaction is a medical emergency, causing difficulty breathing and a dangerously low blood pressure. However, anaphylactic reactions with nasal challenge test are rare and the physician will be monitoring subjects closely after the challenge during the time they are in clinic. If subjects notice symptoms noted above after they have left the clinic, they should call 911 immediately.

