15.3 Time Period, Frequency, and Method of Detecting AEs and SAEs

All AEs occurring after administration of the first dose of study medication and on or before the final assessment must be reported as AEs. All AEs must be recorded irrespective of whether they are considered drug-related.

At each assessment in the period defined above, AEs will be evaluated by the Investigator and recorded.

Any AEs already documented at a previous assessment and designated as ongoing, should be reviewed at subsequent assessments as necessary. If these have resolved, this should be documented. Changes in intensity or frequency of AEs should be recorded as separate events (i.e., a new record started).

The recording of AEs and SAEs are described in Section 14.4 (“Recording of AEs and SAEs”).

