#### **2.4.4. Physical Exam and Nasal Inspection**

Physical examination and nasal inspection data will be presented in data listings.

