## 2.8. Handling Missing Data

Listings will be provided for all data. Descriptive statistics will be provided for all planned visits as provided on the eCRFs. No imputations for missing data will be used in the data displayed in the listings such that the listing will only show “observed data”.

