### Safety and Other Rules

Per the protocol, visits are expected to occur within a given number days of the expected day of the visit. The visits will be analyzed as recorded. Likewise, unscheduled visits will not be reassigned a visit number based on the visit date.

Dates related to the adverse events and medications will be imputed using the rules below in an effort to categorize them properly into the summary tables.

Imputing partial or missing start dates:

- If the year is unknown, then the start date will not be imputed. The date will remain missing.
- If the month is unknown and the year is the same as the first injection date of the study, then impute the month and day of the date to be equal to the first injection month and day. Otherwise, impute the month as January.
- If the day is unknown and the month and year are the same as the first injection date of the study, then impute the day to be equal to the day of the first injection. Otherwise, impute the day as ‘01’.

Impute partial or missing stop dates:

- If the year is unknown, then the stop date will not be imputed. The date will remain missing.
- If the month is unknown, impute the month as December.
- If the day is unknown, impute the day to be the last day of the month.

If an imputed stop date is greater than the date of study completion/discontinuation date of the study, then the imputed stop date will be set equal to the date of completion/discontinuation date.

The imputed dates will be stored in the analysis datasets along with the original dates as recorded by the sites.

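### A subject who needs a new rescue medicine must leave the study, not only stop the spray, so in Part 1 one exit visit without ECG or ABPM replaces the remaining safety visits.

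*Protocol*

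**What the plan says.** Protocol 8.14 allows no rescue medication and sets the consequence of needing it: "Subjects that need to start new rescue medication regimen should be immediately discontinued from study participation and would be considered Early Termination". Protocol 7.3 and 12.6 distinguish subjects who leave the study from those who stop applying the product. They leave withdrawal for interfering therapy to a decision by the investigator with the sponsor.

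For anyone who leaves, Protocol 7.5 provides one visit: "Participants who have discontinued the study early will be evaluated by the Investigator at the Unanticipated Visit". It refers to Appendix A for the content. Neither 10.6.5 nor Appendix A gives an ECG or ABPM at that visit. On labs the documents disagree. The list in 10.6.5 reads "laboratory testing (blood for metabolic panel, hematology, clinical chemistry, liver function test, urinalysis", with no lipid panel, while 11.9 and Appendix A footnote 7 include the lipid panel and both apply to the Unanticipated Visit.

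The Part 1 primary endpoint (Protocol 4.1) is AEs, physical examination and vital signs over 14 days of treatment and up to 28 days of follow-up. SAP 2.8 says "Descriptive statistics will be provided for all planned visits as provided on the eCRFs" and that "unscheduled visits will not be reassigned a visit number based on the visit date". SAP 2.4.4 says "Physical examination and nasal inspection data will be presented in data listings".

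The AE window is stated in two ways. Protocol 15.3 says "All AEs occurring after administration of the first dose of study medication and on or before the final assessment must be reported as AEs". Protocol 12.2 says that Part 1 AEs "during 14 days of treatment and 28 days of follow-up (7 and 28 days after the last dose of the study) will be recorded", and 14.4.2 analyses AEs through 28 days after the last dose.

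**The concern.** The trigger for leaving is a need for treatment, so the visits that go missing may be related to how the subject was doing on the product. The study exists first to describe safety, the active groups have 8 subjects each, and Protocol 14.5.1 rules out imputation. Ending dosing has an obvious rationale. Ending observation does not follow from it, and the protocol already has a category for stopping product without leaving.

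Two parts of the primary endpoint, vital signs and examination, depend on the scheduled visits. ECG, ABPM and labs are safety parameters in SAP 2.4 but are not named in that endpoint. For AEs, the concern is narrower. Because 15.3 does not define the final assessment, a site could take the exit visit as the end of collection for new non-serious AEs, although 12.2 and 14.4.2 imply 28 days after the last dose.

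**Working it through.** **Plan's own figure.** Protocol 14.1 enrols 24 for 20 Part 1 completers at 16.7% dropout. With d = 4/24, 20/(1 − 4/24) = 24.0; with the rounded rate, 20/(1 − 0.167) = 24.01. The figure reproduces. Each cohort plans 8 active subjects for 7 completers, an allowance of 8 − 7 = 1 loss per active group.

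**Inputs.** Scheduled post-baseline assessments come from Protocol 10.5.6, 10.5.8 and 10.5.9. Exit-visit content comes from 7.5, 10.6.5, 11.9 and Appendix A. The clinic blood pressure and heart rate taken at Week 2 ABPM placement (10.5.5) are not counted as a separate set.

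**Formula.** Net loss = scheduled sets still to come − sets obtained at the exit visit.

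| Assessment | Scheduled after baseline | At exit visit | Exit before Day 14 | Exit Days 14–21 | Exit after Day 21 |
|---|---|---|---|---|---|
| Vital signs, exam, nasal inspection | 3 (Days 14, 21, 42) | 1 | 3 − 1 = 2 | 2 − 1 = 1 | 1 − 1 = 0 |
| Labs | 2 (Days 14, 42) | 1 | 2 − 1 = 1 | 1 − 1 = 0 | 1 − 1 = 0 |
| ECG | 2 (Days 14, 42) | 0 | 2 | 1 | 1 |
| ABPM | 1 (Day 14) | 0 | 1 | 0 | 0 |
| Lipid panel, by 11.9 and Appendix A | 2 (Days 14, 42) | 1 | 1 | 0 | 0 |
| Lipid panel, by 10.6.5 | 2 (Days 14, 42) | 0 | 2 | 1 | 1 |

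Where the net loss is zero, the exit assessment is still taken earlier than Day 42.

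**Effect on by-visit summaries.** This depends on how the exit visit is entered.

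- If it is recorded as unscheduled, SAP 2.8 leaves every missed planned visit empty for that subject. For the three exit periods in order, vital signs are missing at 3, 2 and 1 visits, labs at 2, 1 and 1, ECG at 2, 1 and 1, and ABPM at 1, 0 and 0.
- If it is entered in place of one missed visit that includes labs, the vital-sign counts fall by one to 2, 1 and 0, and the lab counts to 1, 0 and 0. ECG and ABPM do not change.

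Physical examination and nasal inspection are only listed, so for them the loss is of later listed records.

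**Share of a dose group.** One exit is 1/8 = 12.5% of enrolled active subjects at a dose, or 1/7 = 14.3% of target completers, and uses that group's whole planned allowance of one.

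**The case against.** Several counter-arguments stand in whole or part.

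- **AE reporting is little affected.** AEs are summarised by subject incidence, not by visit, so an event that leads to rescue is counted and also appears in the tables of AEs leading to discontinuation. A reader might infer that the leading component of the primary endpoint is lost. The documents do not support that; only new non-serious AEs after exit are in doubt.
- **Follow-up does not end.** Protocol 12.6 asks for full evaluation when possible. Sections 7.5 and 15.4 follow ongoing AEs thought possibly related. Section 15.7, although placed under SAE reporting, asks for the outcome of any AE to be followed. Section 12.2 adds a 180-day contact for SAEs and new-onset conditions. None of this supplies scheduled vital signs or ECGs.
- **The lipid panel is not clearly missing.** A reader of 10.6.5 alone would say that it is. Sections 7.5 and 12.6 send the site to Appendix A, which includes it, so this is an inconsistency between lists.
- **The gaps in the summaries are conditional.** The eCRF is not available, SAP 2.8 analyses visits as recorded, and early termination is a defined abbreviation in the protocol. It cannot be shown that the exit visit would be entered as unscheduled.
- **The trigger is narrow.** Section 8.12 provides for recording medicines given for AEs, so treating an AE need not mean exit. Part 1 enrols people without allergy symptoms.
- **Removing subjects on confounding medicines is defensible.** Section 8.13 notes that NSAIDs and corticosteroids may affect blood pressure. But confounded values can be flagged and set aside, whereas values never taken cannot be recovered.
- **Staying on visits does not restore everything.** Section 11.5.2 ties ABPM to dosing at hookup, so an off-product subject cannot give a comparable recording. Days 21 and 42 also stop being 7 and 28 days after the last dose.

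**Conclusion.** The point holds as a low-cost improvement to a design choice. It does not show that the Part 1 safety evaluation is invalid. Section 8.14 requires exit where stopping product would do, and one visit without ECG or ABPM takes the place of up to three scheduled visits. The loss is largest for an exit before Day 14 and small afterwards.

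The 12.5% figure applies to descriptive by-visit summaries of one active group at each missed visit. It assumes a full group of 8 and an exit visit recorded as unscheduled. The documents do not say how often rescue would be needed, so the number affected cannot be computed; it is probably small. That the missingness is informative is plausible from the trigger, not demonstrated. No sample-size calculation depends on these values: SAP 2.7 says the size has no statistical basis.

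**What to change.** In Protocol 8.14, 7.5 and 12.6, state that a subject who starts a rescue medicine stops investigational product but stays in the remaining scheduled safety visits unless consent is withdrawn.

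- Part 1: vital signs, examination and nasal inspection at Days 14, 21 and 42, with labs and ECG at Days 14 and 42, as still applicable. Do not require ABPM off product.
- Part 2: the Visit 4 safety assessments, without the allergen challenge.
- Flag data taken after the medicine and record time since last dose.
- In 15.3, collect AEs from anyone who still leaves early through at least 28 days after the last dose, to match 12.2 and 14.4.2.
- Reconcile the lab list in 10.6.5 with 11.9 and Appendix A.

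The cost is a protocol amendment with IRB approval, a data flag and a time-since-dose field. The visits are already scheduled. The downside is that some follow-up values, notably blood pressure, will be taken off product and under a confounding medicine, and should be read that way.
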